11.5. Follow-up for Adverse Events

Throughout the study to the final study visit, all AEs will be followed until they resolve or become chronic (as judged by the investigator).

At the final study visit, new AEs, as well as follow-up information for continuing AEs, will be recorded in the CRF and source document. Beyond the final study visit, AEs will be followed only until 30 days after the final study treatment.

If a serious AE (defined in Section 11.3) is unresolved within 30 days after the final study visit, it will be followed by the investigator until it resolves or becomes chronic (as judged by the investigator). Follow-up data for such SAEs will be recorded on the CRF and source documents and reported to the safety contacts until the event resolves or becomes chronic (as judged by the investigator) or until 30 days after the final study visit, whichever comes first.

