11.3.1. Serious Adverse Events

Any SAE occurring in this study must be reported immediately (within 24 hours) to the sponsor safety contact using the SAE Form provided by the sponsor.

Patients enrolled retrospectively may have experienced an SAE after ILUVIEN administration but prior to providing informed consent for the study. These "retrospective" SAEs should be reported to the sponsor, via the SAE form, as soon as possible after the patient has provided informed consent for the study.

The investigator or sponsor, if appropriate, must also submit documentation of the following to the Ethics Committee (EC):

Center-specific SAEs and follow-up to these SAEs: The type of SAE that must be submitted (e.g., all SAEs or only suspected SAEs), as well as the required timing of submission (e.g., within 15 days of occurrence), is defined by the EC or regulatory authorities.

All reportable SAEs from the study: The sponsor will provide the investigator with documentation of reportable SAEs, from all study centers, during the conduct of the study.

The investigator should ensure that the patient receives appropriate medical treatment and that the patient is followed up until the SAE resolves or becomes chronic, as defined in Section 11.5.

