11.3.2. Other Clinically Significant Adverse Events

Serious ocular adverse events include the following:

• Any ocular surgical intervention (e.g., cataract surgery, glaucoma surgery).

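### Section 11.5 stops recording an open SAE on the day its extended follow-up begins, and ties post-visit AE follow-up to the last implant instead of the last visit

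*Protocol*

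**What the plan says.** Protocol Section 11.5 requires all AEs to be followed up to the last visit, and then states: "At the final study visit, new AEs, as well as follow-up information for continuing AEs, will be recorded in the CRF and source document". Two rules govern what happens afterwards.

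- **AEs.** "Beyond the final study visit, AEs will be followed only until 30 days after the final study treatment". The anchor is the last treatment.
- **SAEs.** The condition is "If a serious AE (defined in Section 11.3) is unresolved within 30 days after the final study visit". For such an event, "it will be followed by the investigator until it resolves or becomes chronic", in the investigator's judgment and with no time limit. The next sentence has the data for these SAEs recorded and reported until they resolve or become chronic, "or until 30 days after the final study visit, whichever comes first". The anchor is the last visit.

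Section 11.3.1 separately asks the investigator to ensure that "the patient is followed up until the SAE resolves or becomes chronic, as defined in Section 11.5". Section 11.3.2 classes any ocular surgery, including cataract and glaucoma surgery, as a serious ocular event, so these events come under the SAE rule.

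**The concern.** The AE sentence reads like one written for a repeat-dosing trial, where the last dose falls close to the last visit. Here the product is an implant that releases drug for about three years, with retreatment possible after Month 12, so the last treatment and the last visit are usually far apart. The SAE paragraph asks for follow-up beyond day 30 but closes the record at day 30.

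Long-term safety is a stated objective (Section 4), and the study is a condition of the marketing authorisation (Section 3). Patients implanted within about three years of close are still exposed when the study ends. At stake are the final outcome and resolution date of events open at that point. Section 11 requires the date of resolution to be recorded, or the fact that the event is continuing or chronic. Sites that follow different sentences of Section 11.5 would return different data for the same situation.

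**Working it through.** The protocol gives no figure for this point. Its one statistical figure, in Section 12.1, reproduces: 1 − 0.997^550 = 0.808, against a stated value of about 80%. That figure concerns whether an event is reported at all, so the close-out rules do not bear on it. The 550 is used below only for scale.

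**SAE rule.** Count days from the final visit and let R be the day on which the SAE resolves or becomes chronic.

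- Trigger for extended follow-up: open at day 30, so R > 30.
- Investigator follow-up ends at R.
- Recording and reporting end at min(R, 30). For every SAE that meets the trigger, this is 30.
- Recorded time from the final visit: up to 30 days.
- Recorded time after the trigger: 30 − 30 = 0 days.
- Followed but unrecorded: R − 30 days, which is always positive.

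Section 11.3.1 agrees with the follow-up sentence. It conflicts only with the recording cap, but its cross-reference sends sites to the paragraph that contains the conflict.

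**AE rule.** Let g be the number of days from last treatment to final visit. The post-visit window is W = max(0, 30 − g).

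| g (days) | 0 | 15 | 29 | 30 | 180 | 360 |
|---|---|---|---|---|---|---|
| W (days) | 30 | 15 | 1 | 0 | 0 | 0 |

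With visits at least every 6 months and a month defined as 30 days (Section 10), W is zero for anyone whose final visit is the first 6-month visit after the last implant, or any later one. Retrospective patients are treated before enrolment and must enrol at least one year before the planned end (Section 6.4). Any of them who stays to the end without a further implant therefore has g of at least 360 days and W = 0.

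**Share of patients with W > 0.** The protocol gives neither a retreatment rate nor a distribution of implant dates, so these are assumptions. The study length T is taken as both 6.5 years (Sections 4, 12.3 and 13) and 5 years (still in Sections 3, 5.1, 6.5 and 10), with 360-day years and the final visit at study end.

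- Last treatments uniform over the whole study, share = 30/T: 30/2340 = 1.28% (7.1 of 550) and 30/1800 = 1.67% (9.2 of 550).
- Only a retreated fraction r counts, with last retreatments uniform from Month 12 to the end, share = r × 30/(T − 360). At 6.5 years, r = 10% gives 0.15% (0.8 of 550) and r = 50% gives 0.76% (4.2 of 550). At 5 years the same fractions give 0.21% (1.1 of 550) and 1.04% (5.7 of 550).

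The range is about 1 to 9 of 550. Neither scenario counts patients who withdraw within 30 days of an implant. The second also leaves out late first implants and late fellow-eye implants.

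**The case against.** The strongest reply is that both rules can be read more kindly.

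- **The AE sentence is coherent.** AEs are followed and updated to the last visit. After that, only patients treated shortly before it get extra time. Such patients can exist through late first treatment, retreatment, fellow-eye treatment (Section 8) or early withdrawal (Section 6.5). This stands in part: the rule does not cancel itself. But it describes a post-visit period that almost no patient has, and it uses a different anchor from the paragraph that follows it.
- **Section 11.3.1 sets a care duty, not a recording period.** This stands. The conflict is with the recording cap in Section 11.5, not with the follow-up sentence there.
- **The planned analysis barely depends on this.** Section 12.5 counts patients with at least one occurrence and names no analysis of resolution or duration. Events open at the last visit are already on the CRF. This stands, and it limits the importance of the point.
- **A 30-day tail would not cover the remaining drug release.** This also stands. The three-year release explains why events may be open at close; it is not a harm that re-anchoring the AE window would cure.
- **A final report needs a data cut-off.** This stands, and the fix has to allow for it.

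A reader might infer that all events open at study end are followed or recorded for zero days. The text does not support that for SAEs: the investigator follows them without limit, and their data can be recorded for up to 30 days after the last visit. Zero applies only to recording after day 30. A reader might also infer that event incidence is biased. It is not, beyond trivial effects, because new and continuing AEs are recorded at the final visit.

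**Conclusion.** Section 11.5 is wrong as written, and should be corrected, in two respects.

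1. For every SAE that meets its own trigger, recording stops when the extended follow-up starts, so no later outcome reaches the CRF or the safety contacts. This follows from the wording alone and needs no assumption. How many SAEs are affected cannot be estimated from the protocol.
2. The post-visit AE window has the wrong anchor and is empty for nearly all patients. That it is empty when the last implant was 30 or more days before the final visit is exact. The figure of about 1 to 9 of 550 patients with any window rests on the assumed implant dates and retreatment rates above.

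The loss is confined to outcome and resolution data and to consistency between sites. The planned incidence summaries and the sample-size statement are not affected.

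**What to change.** Reconcile Sections 11.3.1 and 11.5 into one data rule.

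- Anchor the AE sentence to the final study visit, as the SAE sentences already are.
- Let recording and reporting of SAEs open at day 30 run as long as the follow-up already stated for them, to resolution or chronicity, so that the day-30 cap no longer closes the record when the follow-up begins.
- Keep a database cut-off for the final report. Outcomes that arrive after it go to the safety contacts and the safety database.

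This concerns data capture only and changes no treatment or clinical care. The cost is about two sentences in an amendment and a few extra follow-up records after study close.

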11.6. Reporting of Product Complaints

Product complaints include quality complaints reported in writing, electronically, or orally involving the use or attempted use of this product that identify any defects in the product (failure of the applicator to deliver the implant, etc.), or defect of the product (dispensing characteristics, labeling, packaging, etc.).

Any product complaint should be reported by email to the sponsor's Quality Assurance Department ([contact]) or fax ([contact]) within 24 hours.

Patients enrolled retrospectively may have experienced a product complaint after ILUVIEN administration. These "retrospective" product complaints should be reported to the sponsor as soon as possible after the patient has provided informed consent for the study.

The preferred method is via email. The complaint report should include the following information:

- ILUVIEN Lot Number
- ILUVIEN Expiration Date
- Investigator name, study center name, and contact number (phone, email address)
- Date the complaint occurred
- Brief description of the complaint

• Patient involved? (yes or no); if yes, were any AEs associated with the complaint? (yes or no), (If an AE is associated with the complaint, refer to Section 11.1).

If the complaint falls under these two categories (1) bent/damaged needle and/or (2) difficulty in actuating the applicator button to insert the drug implant, the sponsor's Quality Assurance Department will issue an identification sequence to be used prior to sending the ILUVIEN applicator in its original container (tray and carton) which initiated the complaint to:

Quality Department AndersonBrecon (UK) Limited [name]

Any complaint about this product must be reported regardless of whether the defect or deficiency had any effect on a patient or on study personnel.

12. STATISTICS

12.1. Sample Size

The sample size for this registry study was determined in conjunction with the United Kingdom MHRA during the marketing authorisation application review. A sample size of 550 patients will provide approximately 80% probability of detecting one or more reports of any adverse event with a true underlying 5-year incidence of 0.3% assuming a 0.050 2-sided significance level.

12.2. Data Sets to be Analyzed

The safety data set will include data from all patients who receive an ILUVIEN treatment, and for whom at least one post-baseline safety follow-up is obtained. All patient data will be used; no data will be excluded because of protocol violations.

12.3. Schedule of Analyses

The total study duration will consist of 6.5 years from the date of enrolment of the first prospectively enrolled patient. Formal study reports summarizing the study data will be prepared after Year 3 of the trial and after the study has completed. Analyses will also be conducted on an "as-needed" basis for marketing purposes and for Periodic Safety Update Reports.

12.4. Analysis of Demographic and Baseline Data

The demographic and baseline characteristics will be summarized for the Safety data set. These data will be presented in tabular summaries to describe the patients enrolled into the study. Continuous variables will be summarized by mean, standard error, standard deviation, median, minimum, and maximum; and by counts and percentages for categorical variables.

12.5. Safety Variables

Safety analyses will be performed on all patients who receive ILUVIEN. Ocular safety will be assessed by evaluating ocular adverse events, retreatments with ILUVIEN, visual acuity, intraocular pressure, and concomitant ocular medications and therapies. If a patient receives bilateral ILUVIEN, then each eye will be summarized.

Systemic safety will be assessed by evaluating non-ocular adverse events, and concomitant non-ocular medications and therapies.

Adverse events will be summarized by presenting the number and percentage of patients having at least one occurrence of any adverse event during the study, having at least one occurrence of an adverse event within each system organ class, and having at least one occurrence of each individual adverse event. Each reported adverse event will be coded to a corresponding preferred term from the MedDRA coding dictionary.

For continuous safety variables, e.g., visual acuity, intraocular pressure, the observed and change from baseline values will be summarized descriptively (n, mean, standard error, standard deviation, median, minimum, maximum and frequency distribution) at each visit.

Specific adverse events of interest will be tabulated: IOP-related and cataract-related events, procedural complications such as endophthalmitis, retinal tears, retinal detachments, vitreous

haemorrhage or vitreous detachments. Potential safety risks that have not been observed in clinical trials will also be monitored such as, retinitis secondary to reactivation of latent viral infections or other ophthalmic infections, potential systemic events associated with the use of corticosteroids or haemorrhagic events associated with the concurrent therapy with anticoagulant medications. Information on retinal ischaemia, removal of the implant, and long-term safety data will be evaluated.

An evaluation of safety in patients who have received ILUVIEN in both eyes during the study will also be performed.

Summaries for specific subgroups of patients will be performed on all safety data. Analyses will be performed to determine the effect of treatment within specific subgroups of interest. Subgroups to be considered include:

- Patients diagnosed with diabetic macular oedema for 3 or more years
- Patients diagnosed with diabetic macular oedema for less than 3 years
- Patients not diagnosed with diabetic macular oedema
- Patients receiving a single ILUVIEN during the study
- Patients receiving more than a single ILUVIEN in the same eye during the study
- Patients receiving ILUVIEN bilaterally at any time during the study
- Patients who are pseudophakic at baseline in the eye receiving ILUVIEN
- Patients who are phakic at baseline in the eye receiving ILUVIEN
- Women who are pregnant at enrolment or who become pregnant during the course of the study
- Women who are lactating at enrolment or who begin lactating during the course of the study
- Paediatric patients, defined as patients less than 18 years of age on the day of ILUVIEN treatment

If there are a sufficient number of patients enrolled with diagnoses other than diabetic macular oedema, e.g., retinal venous occlusion, uveitis, separate summaries will be prepared for each diagnosis.

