4. STUDY OBJECTIVES AND PURPOSE

The study will assess the safety and usage in patients treated with ILUVIEN.

The specific objectives include the study of known safety risks of cataract formation or progression, increased intraocular pressure (both within 30 minutes post-treatment and long-term), changes in intraocular pressure and development of glaucoma, procedural complications such as endophthalmitis, retinal tears, retinal detachments, vitreous haemorrhage or vitreous detachments. Potential safety risks that have not been observed in clinical trials will also be monitored such as, retinitis secondary to reactivation of latent viral infections or other ophthalmic infections, potential systemic events associated with the use of corticosteroids or haemorrhagic events associated with the concurrent therapy with anticoagulant medications. Unknown safety risks will be captured as well. Information on significant retinal ischaemia, removal of the implant, long-term safety data, and repeat use will be evaluated. An evaluation of safety in patients who have received ILUVIEN in both eyes during the study will also be performed. The change from baseline visual acuity (VA) will be evaluated.

Any use in paediatric patients, pregnant or lactating women and off-label use for other retinal oedema conditions will be reported. It should be understood that the sponsor does not advocate the use of ILUVIEN for any indication other than that which is specified on the Summary of Product Characteristics (SPC). However, it is also known that, in clinical practice with marketed products, off-label use is common. Therefore, the sponsor intends to collect safety data of any patient treated with ILUVIEN.

This study will collect data for 6.5 years from the date of enrolment of the first prospectively enrolled patient. As a result, patients will have varying numbers of study visits.

Amendment 1 to this protocol allows for the retrospective enrollment of patients treated with ILUVIEN prior to enrolment into the study provided that they satisfy the same entry criteria as applied to patients enrolled prospectively.

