5. INVESTIGATIONAL PLAN

5.1. Overall Study Design

This study is a non-randomized, open label, uncontrolled, multi-centre, study in which safety data on at least 550 patients who are treated with ILUVIEN for any reason will be collected over a 5 year period from the date of enrolment of the first prospectively enrolled patient. Patients should be treated and monitored in accordance with the Summary of Product Characteristics; however, any patient who is treated with ILUVIEN can be enrolled in the study.

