6.4. Retrospective Enrolment Criteria

Patients treated with ILUVIEN prior to study initiation may be included provided they satisfy the inclusion and exclusion criteria, where applicable, as well as, the following requirements:

- 1. The site is allowed to enrol a patient who was treated with ILUVIEN no more than 36 months prior to bringing the patient in for their first study visit.
- 2. The eligible patient must meet the data requirements as specified in the protocol, i.e., baseline data collected within 7 days prior to treatment with ILUVIEN and additional data subsequently collected approximately every 6 months thereafter until enrolment into the study.
- 3. The eligible patient must be enrolled at least one year prior to the planned end of the study.

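### Section 12.5 reports adverse events as crude percentages under very unequal follow-up, so the figures are not incidences at 5 years or any other fixed time

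*Protocol*

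**What the plan says.** Section 12.5 fixes the adverse event summary as "presenting the number and percentage of patients having at least one occurrence of any adverse event during the study", and repeats it by system organ class and by individual event. Events of interest (IOP-related, cataract-related, procedural complications) are to be tabulated. The protocol names no person-time rate, time-to-event estimate or fixed window for adverse events.

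Follow-up is unequal by design:

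- Section 12.3: "The total study duration will consist of 6.5 years from the date of enrolment of the first prospectively enrolled patient". Section 5.1 instead has data collected "over a 5 year period from the date of enrolment of the first prospectively enrolled patient". Under either, the end is one calendar date for everyone.
- Section 4 accepts the consequence: "As a result, patients will have varying numbers of study visits".
- Section 6.4 admits patients treated up to 36 months before their first study visit, and adds: "The eligible patient must be enrolled at least one year prior to the planned end of the study". No such minimum is stated for prospective patients.
- Section 6.5 does not replace withdrawals. Under Section 12.2 a single post-baseline safety follow-up puts a patient in the safety set.

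The aims are tied to time. Section 12.1 sizes the study on "any adverse event with a true underlying 5-year incidence of 0.3" per cent, and Section 4 lists long-term safety and repeat use among the matters to be evaluated. Sections 12.3 and 12.5 add a report after Year 3 and summaries by subgroup, including one implant versus more than one in the same eye.

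**The concern.** A patient with a few months of observation and one with more than six years count equally in the denominator. The resulting percentage is an average of risks over whatever follow-up happened to accrue. It would change with faster enrolment or better retention even if the implant's safety did not.

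Two uses are exposed. First, a reader of the registry reports may take the percentage as the risk over the period on which the study was sized. Second, the subgroup tables invite comparison. The Synopsis allows retreatment only after the Month 12 assessments, so repeat-implant patients must have remained under observation beyond that point, while early withdrawals and late entrants fall mostly in the single-implant group. A difference in percentages then partly measures follow-up length. The Year 3 report is likely to be hit hardest, since many patients will have entered recently.

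**Working it through.** **1. The plan's own figure.** Section 12.1 gives 550 patients, a 5-year incidence of 0.3% and about 80% probability of at least one report. 1 − 0.997^550 = 0.808, so the figure reproduces. The formula gives every patient the full 5-year risk.

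**2. Set-up for the crude percentage.** The protocol gives no accrual pattern, loss rate or hazard shape, so these are assumptions. With a constant hazard λ = −ln(1 − r5)/5, where r5 is the true 5-year risk, and follow-up uniform from a to b years, the expected crude proportion is

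1 − [exp(−λa) − exp(−λb)] / [λ(b − a)].

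With loss at rate μ per year, put k = λ + μ:

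(λ/k) × {1 − [exp(−ka) − exp(−kb)] / [k(b − a)]}.

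**3. Worked case.** r5 = 20% gives λ = 0.04463. For a = 1 and b = 6.5: exp(−0.0446) = 0.9564, exp(−0.2901) = 0.7482, and the difference divided by 0.2455 is 0.848. The crude figure is 15.2%. With μ = 0.05 it is 13.7%. In this scenario 1.5/5.5 = 27% of patients reach 5 years and 2/5.5 = 36% have under 3 years.

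**4. Other follow-up patterns, true 5-year risk 20%.**

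| Follow-up (uniform) | No loss | 5% loss per year |
|---|---|---|
| 1–6.5 years | 15.2% | 13.7% |
| 1–5 years (5-year study end) | 12.4% | 11.4% |
| 3.5–6.5 years (accrual in 3 years) | 19.9% | 17.7% |
| 1–9.5 years (some with long look-back) | 20.4% | 17.7% |
| 4–9.5 years (many with long look-back) | 25.8% | 22.0% |

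A true 50% over 1–6.5 years appears as 39% without loss and 36% with it.

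**5. Shape of the risk (1–6.5 years, no loss).**

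- Risk only after year 3, at 0.3% by 5 years: the crude figure is about 56% of the 5-year incidence, against 75% for a constant hazard.
- A small risk accruing evenly over the first 3 years and then stopping: the share captured is (1.333 + 3.5)/5.5 = 88%.
- Events around the injection: nearly all captured.

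**6. Year 3 report.** With entry uniform over 3 years and λ = 0.04463, the true 3-year risk is 1 − exp(−0.1339) = 12.5%. The crude figure is 1 − 0.1253/0.1339 = 6.4%. Look-back shrinks this: if every patient brought 1.5 earlier years (follow-up 1.5–4.5 years), the crude figure would be 12.5%.

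**7. Subgroup contrast (illustration).** With the same hazard in both groups, 2 years of follow-up gives 1 − 0.8^(2/5) = 8.5% and 5 years gives 20%. Follow-up alone produces that gap.

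**The case against.** Four points deserve weight.

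- The SAP is not at hand, and rates per patient-year, Kaplan-Meier methods and confidence intervals often sit there. A reader might infer that no time-based analysis of adverse events is planned at all; the protocol does not support that. What stands is that the protocol does name a summary for adverse events, and the one it names does not suit the follow-up.
- The protocol never calls the percentage a 5-year incidence; it says only that events occurred during the study. The sample size statement concerns detecting at least one report, for which a count suffices. A reader might infer that the 80% is wrong. It is arithmetically right for patients who carry the full 5-year risk. Under uniform follow-up of 1–6.5 years the probability would be about 71% (constant hazard), but that is a separate sample size question.
- It is tempting to say that the percentages necessarily understate late risks. The documents do not support this. Direction depends on accrual, loss and look-back, none of which the protocol quantifies, and step 4 shows results from well below to above the 5-year risk.
- No formal test between subgroups is stated, and IOP and visual acuity are summarised at each visit, so those are described over time. That limits the damage but does not repair the adverse event tables.

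**Conclusion.** The point holds as a should-fix. The crude percentage in Section 12.5 is not a 5-year or any fixed-time incidence; it depends on accrual and loss, and contrasts such as single versus repeat implant are confounded by follow-up length. That conclusion needs no assumption beyond the unequal follow-up that the protocol itself describes.

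The size does need assumptions. For a true 5-year risk of 20%, plausible patterns run from about 11% (5-year end, with loss), through near nil bias (3-year accrual, no loss), to about 26% (many long retrospective histories, no loss). Events near the procedure are little affected. The Year 3 report is probably the most affected, less so if many patients bring look-back time.

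**What to change.** In Section 12.5:

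- For the adverse events of interest, add cumulative incidence from the implant date at fixed times (for example 1, 2, 3 and 5 years) with 95% confidence intervals and numbers at risk. Censor at last follow-up and treat death as a competing event (Aalen-Johansen).
- Do not treat explantation as a competing event for adverse events that can still be observed after it.
- Handle retrospective patients by delayed entry at consent, or show them separately from prospective patients. They had to be available to consent after treatment, so an ordinary curve from implantation counts time in which they could not have died or been lost. Delayed entry leaves events before consent out of the curve; they remain in the counts.
- Add events per 100 patient-years for all preferred terms.
- Keep the crude counts and percentages, with total person-time beside them, overall and in each subgroup.

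The dates needed are largely collected already: Section 11 requires onset dates, and treatment and visits are recorded. The cost is a few more tables, and some reported risks may look less favourable.
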